The intervention will use commercially available RS-2 (Hi-Maize) that will be prepared into common bakery items, such as muffins, scones, as well as beverages such as smoothies. Control products will use the same recipe but will be prepared with regular corn starch. The RS will be Hi-Maize, a corn starch made solely from hi-amylose maize. This product is commercially available from, among others, King Arthur Flour, Honeyville and Amazon. It has been used in many published studies⁸⁵⁻⁹³ as well as at least 20 studies currently listed in ClinicalTrials.gov. Dose range has been from 15g/day to 47g/day and study duration from 1 to 8 weeks. Some people may experience flatulence and perhaps some bloating due to the higher fiber content added to their diet, therefore we will have participants do a stepwise escalation that will allow for better adaptation to the target dose of 30g. RS per day. In the first two weeks participants will consume one study food with 15 g RS per day and starting in the third week participants will consume two study foods for a total of 30g RS per day for 6 weeks. Participants will be provided with a variety of options to allow for variety. No other dietary changes will be required. Participants may consume their usual diet and participate in their usual activity throughout the study. All products will be produced at the Human Nutrition Lab in the Fred Hutch Prevention Center. See Figure 2.

Systemic inflammation will be measured as serum C-reactive protein (CRP)/albumin ratio and adiponectin. Insulin resistance will be assessed using the homeostasis model of assessment-insulin resistance (HOMA-IR). Gut microbial community structure (16S rRNA sequencing), and gut metabolites will be compared between intervention and control groups for generation of hypotheses for protective prebiotic effects on gut microbial taxa.

In order to determine whether an RS dietary intervention can potentially affect gastrointestinal tumorigenesis in high-risk individuals, participant fecal microbiota sampled will be transplanted into colorectal tumor-prone mice ([name], UW IACUC protocol # 4418_01).

[figure not shown]
Primary Aim: To determine the feasibility of an 8-week dietary intervention testing foods made with resistant starch compared to foods made with corn starch in patients who have completed treatment for stage I-III colorectal cancer. Feasibility will be assessed based on trial accrual, intervention adherence, and trial retention.

Secondary Aims:

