
1. To assess variability from baseline to 8 weeks in circulating markers of insulin resistance (glucose, insulin and HOMA-IR) and inflammation (CRP, albumin, adiponectin), by randomization arm.
2. To assess variability from baseline to 2 weeks and 8 weeks in gut microbial communities based on 16S rRNA gene sequencing, by randomization arm.
3. To explore whether resistant starch suppresses adenomas/carcinomas in human to mouse Fecal Microbiota Transplantation (FMT) studies.

Randomized, Controlled Trial of Resistant Starch in Stage I-III Colorectal Cancer Survivors Pilot Study: The Fiber for Health After Cancer Study

Figure 2 – Study Design. Note: The Stool Only protocol and companion Intervention Pilot have separate protocols and IRB submissions. [name], Co-PI, will receive human fecal samples for the gnotobiotic mouse experiments under IACUC approval (UW IACUC protocol # 4418_01).

Randomized, Controlled Trial of Resistant Starch in Stage I-III Colorectal Cancer Survivors Pilot Study: The Fiber for Health After Cancer Study

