4. DATA COLLECTION

4.a. CONSENT VISIT

As described in Section 3 above, potential participants schedule a Consent Visit with study staff to take place either in person at the Prevention Center (Arnold Building, Fred Hutch), or telephonically. After reviewing study procedures and being able to ask questions, interested participants will provide written informed consent and height and weight will be collected. After consenting, participants are randomized into the trial using a permuted block design, based on sex and 2 BMI categories (below and equal/above $BMI = 25 \text{ kg/m}^2$). Participants, investigators and study staff will be blinded to randomization condition.

At consent participants are provided with a stool collection kit and written and verbal instructions on their use as well as a blank 1) Food Frequency Questionnaire and 2) a baseline Study Questionnaire to fill out before and bring completed with them to their first intervention visit. Study staff schedule the Intervention Visit 1.

After consent, the following data will be abstracted by study staff from the SCCA/UW Medical Records.

- A. Patient and tumor characteristics at time of **initial (pre-treatment)** presentation at SCCA:
 1. Demographics
 2. Height and Weight
 3. Comorbidities
 4. Resection Surgery Date
 5. Tumor site
 6. T stage
 7. Tumor size
 8. N stage

Randomized, Controlled Trial of Resistant Starch in Stage I-III Colorectal Cancer Survivors Pilot Study: The Fiber for Health After Cancer Study

9. Number of positive nodes
10. Number of total nodes removed
11. Histologic type (i.e. adenocarcinoma)
12. Grade
13. Lymphatic invasion
14. Vascular invasion
15. Perineural invasion
16. Proximal/distal margins
17. Circumferential margin
18. Tumor-infiltrating lymphocytes
19. Peri-tumoral response

B. Colorectal cancer (CRC) treatment information:

1. Neoadjuvant treatment received **prior** to CRC surgery:
 - a. Chemotherapy Y/N and if Y, specific regimen and doses
 - b. Radiotherapy Y/N and if Y, specific regimen and doses
 - c. Dates administered
2. Post-surgical treatment received **after** CRC surgery
 - a. Specific treatment(s) received, dosages, dates
 - b. Associated co-morbidities

4.b INTERVENTION VISIT 1 – START OF INTERVENTION

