We will work with each participant individually to plan how food items will be delivered to them during the course of the study. If a participant is willing and able to come to the Prevention Center once a week or once every 2 weeks, this gives us the opportunity to meet with them face to face and discuss any issues they may be having. If it is not practical for the participant to come to the Prevention Center to receive his/her study food items, we will arrange for delivery of the items via U.S. Mail, Federal Express, in person delivery by study staff, or courier. The HNL has done this procedure for other studies as well. The informed consent form will provide participants the opportunity to consent to their names and delivery addresses to be provided by study staff to the US Postal Service, Federal Express or courier service as needed.

Randomization into active or control group: Participants will be block randomized based on sex and 2 BMI categories. This will ensure that the two intervention arms have similar distributions of patients.

Active and control groups will be blinded, products will be labeled either A or B, and will be unblinded by the Human Nutrition Lab to investigators once study and data analysis has been completed.

Compliance measures: we will provide a calendar-driven, checklist-style daily log for participants to mark having eaten the study food items and, if not completely, how much. This log will also have a place for the participant to record any gastrointestinal issues they may be experiencing.

Interim compliance contacts: the research coordinator will contact the participant (via phone call once weekly through ramp up to 30g daily then every two weeks thereafter through end of study. (See Adherence Call Script, Appendix 15).

Randomized, Controlled Trial of Resistant Starch in Stage I-III Colorectal Cancer Survivors Pilot Study: The Fiber for Health After Cancer Study

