8. DATA ANALYSIS PLAN

Feasibility Endpoints.

Feasibility of the study design and intervention will be assessed based on the following three criteria:

1. Accrual. The accrual rate will be estimated with a target accrual rate of full enrollment within 12 months after study activation.
2. Adherence. Adherence to the intervention will be defined as consuming 75% or more of study foods on $\geq 75\%$ of days from baseline to 8 weeks.

Randomized, Controlled Trial of Resistant Starch in Stage I-III Colorectal Cancer Survivors Pilot Study: The Fiber for Health After Cancer Study

3. **Retention.** Target retention is defined as ≥80% of enrolled participants providing blood and stool samples at 8 weeks.

Secondary Endpoints.

Secondary endpoint analyses will be considered exploratory and will be used to provide effect size estimates to be used in a future trial.

1. Assess variability in biomarkers of insulin resistance and inflammation will be assessed using descriptive statistics.
2. Assess variability in gut microbial communities from human stool samples collected during the study by changes in alpha diversity, global microbial community (beta diversity), and genera in response to the intervention. We will use multivariate and univariate approaches to assess significant changes in the microbiome in response to the intervention.
3. Fecal microbiota from “resistant starch responders” (i.e., individuals with significant resulting elevations in fecal short-chain fatty acids concentrations) will be selected as input samples in gnotobiotic mouse studies, in which mice will be fed diets with or without resistant starch in order to characterize effects on tumorigenesis in an otherwise controlled environment. We predict that the chemoprotective effect of this diet intervention will be dependent upon gut microbial metabolism.

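### Randomization is stratified by sex and BMI category, but Section 8 does not carry these factors into the secondary analyses: a modest, conditional loss of precision, not a bias

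*Combined protocol and SAP*

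**What the plan says.** Section 4.a sets the allocation: "participants are randomized into the trial using a permuted block design, based on sex and 2 BMI categories". The BMI categories are below 25 kg/m² and 25 or above, so there are four strata. Section 5 repeats this and gives the purpose: "Participants will be block randomized based on sex and 2 BMI categories. This will ensure that the two intervention arms have similar distributions of patients". Section 3 explains that height and weight are obtained at the Consent Visit because the randomization needs them; they are self-reported if that visit is by telephone.

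The primary aim (Section 1) has no between-arm contrast: "Feasibility will be assessed based on trial accrual, intervention adherence, and trial retention". The first secondary aim begins "To assess variability from baseline to 8 weeks in circulating markers of insulin resistance" and is to be reported by arm. The second concerns the gut microbial community from baseline to 2 and 8 weeks, also by arm. The Study Overview in Section 1 says that microbial community structure will be compared between the two groups.

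Section 8 gives the analysis. For biomarkers: "Assess variability in biomarkers of insulin resistance and inflammation will be assessed using descriptive statistics". For the microbiome: "We will use multivariate and univariate approaches to assess significant changes in the microbiome in response to the intervention". On purpose: "Secondary endpoint analyses will be considered exploratory and will be used to provide effect size estimates to be used in a future trial". Neither sex, BMI nor strata is named in Section 8.

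**The concern.** Blocking within strata makes the arms alike on sex and BMI category, so differences between strata largely cancel out of the arm difference. An ordinary two-sample standard error, or a test that treats all participants as exchangeable, does not know this and still counts between-stratum variance as noise. If the factors are prognostic, the resulting interval is wider than the design warrants and the test less powerful. A permutation test that moved arm labels across strata would also use allocations that the design would rarely or never produce.

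The outputs at stake are those that Section 8 intends to hand to a future trial: the effect sizes, their precision and the SDs that go with them. Section 8 does not commit the analyst either to using the randomization factors or to leaving them out.

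**Working it through.** **Inputs.** The documents give the two factors and four strata. The available text gives no sample size (accrual is tied only to full enrollment), block size, SD or prognostic strength, so there is no figure of the plan's own to reproduce. Assumptions: N = 40 analyzed (20 and 30 also run); blocks of 4; sex 50:50; BMI of 25 or above in 60%; sex and BMI acting additively; R² = share of outcome variance explained by the two factors, 0 to 0.30; no true arm effect; 4,000 simulated trials per setting.

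**Step 1: week-8 level, no baseline in the model.** With total variance 1 and equal arms, the ordinary squared standard error of the arm difference is 4/N. Under balance within strata the actual variance is about (4/N)(1 − R²). So the unadjusted interval is too wide by roughly 1/√(1 − R²).

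Hand check at N = 40: √(4/40) = 0.316. The unadjusted 95% half-width is 0.316 × 2.024 = 0.640. Adjusted, at R² = 0.30, it is 0.316 × √0.70 × 2.028 = 0.537.

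Simulation at N = 40 (half-widths in SD units; adjusted = sex and BMI category as main effects):

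| R² | 1/√(1 − R²) | Unadjusted | Adjusted | Ratio | Coverage unadjusted / adjusted |
|---|---|---|---|---|---|
| 0 | 1.00 | 0.638 | 0.640 | 0.997 | 94.8% / 94.8% |
| 0.05 | 1.03 | 0.637 | 0.623 | 1.02 | 95.6% / 95.1% |
| 0.10 | 1.05 | 0.637 | 0.606 | 1.05 | 95.8% / 94.8% |
| 0.20 | 1.12 | 0.640 | 0.574 | 1.11 | 96.6% / 94.8% |
| 0.30 | 1.20 | 0.641 | 0.537 | 1.19 | 98.0% / 95.2% |

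The unadjusted interval over-covers; it does not under-cover.

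**Step 2: baseline value in the model.** Aims 1 and 2 concern change from baseline, so this case is closer to the plan. Assume that stratum effects are equal at both times and that the within-stratum correlation between baseline and follow-up is ρ. The residual variance is

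- without strata: 1 − (R² + (1 − R²)ρ)²
- with strata: (1 − R²)(1 − ρ²)

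The ratio simplifies to 1 + R²(1 − ρ)/(1 + ρ).

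| ρ | R² = 0.10 | R² = 0.20 | R² = 0.30 |
|---|---|---|---|
| 0.3 | 1.054 | 1.108 | 1.162 |
| 0.6 | 1.025 | 1.050 | 1.075 |
| 0.8 | 1.011 | 1.022 | 1.033 |

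The variance gain is about 1% to 16%. In interval width, √1.011 to √1.162, it is about 0.5% to 8%.

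**Step 3: change scores.** If the stratum effects are equal at both times, they cancel from the change, the factors explain nothing, and the R² = 0 row applies: no gain.

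**Step 4: why the baseline value belongs in the model.** At R² = 0.20 and ρ = 0.6, adjusting for strata alone leaves residual variance 1 − 0.20 = 0.80. Baseline alone leaves 1 − (0.20 + 0.80 × 0.6)² = 1 − 0.68² = 0.54. Both together leave 0.80 × (1 − 0.36) = 0.51. Strata without baseline would hand on a larger SD than baseline without strata.

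**Step 5: cost if the factors are not prognostic.** At N = 20 and R² = 0 the half-width goes from 0.932 to 0.950, about 1.9% wider; a second simulation gave 1.6%. At N = 40 it is under 1%. Fitting all four strata separately at N = 20 costs about 3% (0.962 against 0.932).

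**The case against.** The strongest objection is that the plan describes almost nothing that could be wrong in this way. Biomarkers get descriptive statistics only, with no between-arm interval. The microbiome wording names no permutation test and excludes no covariates; permutation methods appear only in Section 1, for the group's previous studies. The secondary analyses are declared exploratory, nothing in the documents shows that sex or BMI predicts these outcomes, and any error is on the conservative side. All of this stands, and it limits the point to a gap in specification with a conditional loss of precision. It does not remove the gap: item 2 does plan to assess significance, Section 1 plans a comparison between groups, and the results are to feed a future trial.

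A reader might also infer that the pilot's SDs will be inflated and that a trial sized on them would be 12% to 44% too large. The documents do not support this. Stratified allocation balances the arms but removes no variance from individual outcomes, so a raw by-arm SD is a correct marginal SD. It exceeds what a future trial needs only if that trial adjusts for the same factors, and the documents do not describe its analysis. The 12% to 44% range also belongs to week-8 levels without baseline adjustment at R² from 0.10 to 0.30, not to change from baseline.

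**Conclusion.** The point holds as a minor to moderate efficiency and specification gap. The randomization uses sex and BMI category; Section 8 does not say that the secondary between-arm estimates or tests will. There is no bias, no inflated false-positive rate and no effect on accrual, adherence or retention.

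The size depends on assumed N, block size, stratum shares, R² and ρ: intervals about 5% to 19% wider for unadjusted week-8 levels, a variance gain of about 1% to 16% once baseline is in the model, and possibly nothing for change scores. It would be wrong to read this as a finding that an unstratified interval or a free permutation test has been specified; Section 8 is silent on both.

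**What to change.** In Section 8, secondary items 1 and 2, add:

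- **Biomarkers and alpha diversity:** beside the raw by-arm summaries, report the arm effect with its 95% confidence interval and the residual SD from a linear model of the follow-up value on arm, baseline value (where collected), sex and BMI category. Enter sex and BMI category as main effects, using the category applied at randomization.
- **Beta diversity:** include sex and BMI category as terms and, if a permutation test is used, permute arm labels by participant only within the four strata.
- **Genera:** use the same two covariates.

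Section 4.b allows Visit 1 by telephone without the baseline blood draw. The text should therefore say how participants with no baseline biomarker value enter the model; sex and BMI category are available for everyone randomized.

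The cost is a few sentences and two degrees of freedom. No new data, visits or participants are needed. If the factors prove not to be prognostic, intervals are about 1.6% to 1.9% wider at N = 20 and under 1% wider at N = 40.

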5. INTERVENTION

Active group: Resistant Starch @ 15g/day during weeks 1 and 2, and @ 30g/d for weeks 3-8 (8 weeks total on study). If participant is not able to tolerate the higher doses they may stay at the maximum tolerated dose for the remainder of the study. (See Dosage Modification Instructions in Section 6, below). The Resistant Starch will be Hi-Maize, a RS2 corn starch from hi-amylose maize. This product is commercially available from, among others, King Arthur Flour, Honeyville, Amazon. It has been used in many published studies⁸⁵⁻⁹³ as well as at least 20 studies currently listed in ClinicalTrials.gov. The dosage in our study is comparable to other studies and the product is well tolerated with the main issues being gastrointestinal discomforts such as flatulence and feeling bloated. Studies report few dropouts due to these symptoms.

Control group: will receive similar size and number of items as the active group, made with regular corn starch. If participant is not able to tolerate the higher doses they may stay at the maximum tolerated dose for the remainder of the study. (See Dosage Modification Instructions in Section 6, below).

Study Foods will be developed and produced by the Fred Hutch Human Nutrition Lab (HNL). The HNL facility, within the Prevention Center, is 2,900 ft² designed and implemented solely and specifically to conduct human feeding studies. It includes extensive food storage, food preparation, and service areas. Over a third of the square footage is devoted to storage, allowing for the purchase of food in lot-sized amounts, and consists of a walk-in freezer, refrigerator, and dry storage. The food preparation facility includes both cold and hot food preparation and production areas with a gas cook-top, convection ovens, steamers, microwave oven, blast chiller, Mettler-Toledo balances, and heat-sealer. A networked computer system, operated through the Division of Public Health Sciences, is used for data entry, diet development, and HNL food preparation documents. Available nutrition computer software includes ProNutra. Four offices are available for resource staff, including the HNL manager and research assistants. The commercial kitchen is inspected regularly by the Health Department and all workers have food handlers permits. Over the years, the HNL has delivered over 20,000 study participant meals for a variety of feeding studies. The HNL will design recipes for a series of products in order to give participants variety and satisfaction, ie. scones, muffins, puddings and smoothies. Development of the products will happen in conjunction with study investigators to balance nutritional macronutrient balance. Additionally, we will also consult with the SCCA Medical Nutrition Therapy group to obtain feedback on the nutritional needs of colorectal cancer survivors.

Randomized, Controlled Trial of Resistant Starch in Stage I-III Colorectal Cancer Survivors Pilot Study: The Fiber for Health After Cancer Study

Instructions on study food dosing, safe food handling and storage procedures will be provided to participants (see Appendices 13 and 14).

We will work with each participant individually to plan how food items will be delivered to them during the course of the study. If a participant is willing and able to come to the Prevention Center once a week or once every 2 weeks, this gives us the opportunity to meet with them face to face and discuss any issues they may be having. If it is not practical for the participant to come to the Prevention Center to receive his/her study food items, we will arrange for delivery of the items via U.S. Mail, Federal Express, in person delivery by study staff, or courier. The HNL has done this procedure for other studies as well. The informed consent form will provide participants the opportunity to consent to their names and delivery addresses to be provided by study staff to the US Postal Service, Federal Express or courier service as needed.

Randomization into active or control group: Participants will be block randomized based on sex and 2 BMI categories. This will ensure that the two intervention arms have similar distributions of patients.

Active and control groups will be blinded, products will be labeled either A or B, and will be unblinded by the Human Nutrition Lab to investigators once study and data analysis has been completed.

Compliance measures: we will provide a calendar-driven, checklist-style daily log for participants to mark having eaten the study food items and, if not completely, how much. This log will also have a place for the participant to record any gastrointestinal issues they may be experiencing.

Interim compliance contacts: the research coordinator will contact the participant (via phone call once weekly through ramp up to 30g daily then every two weeks thereafter through end of study. (See Adherence Call Script, Appendix 15).

Randomized, Controlled Trial of Resistant Starch in Stage I-III Colorectal Cancer Survivors Pilot Study: The Fiber for Health After Cancer Study

6. DOSAGE MODIFICATION

The dosage of the assigned study food will be modified if needed based on the participant's inability to tolerate the prescribed dosage.

Intolerance is defined as **any grade 3 or higher adverse event (AE) that is possibly, probably, or definitely attributable to the study food product.**

AEs for this study are assessed and graded in accordance with the NCI's Common Terminology Criteria for Adverse Events (CTCAE), version 5.0:

https://ctep.cancer.gov/protocoldevelopment/electronic_applications/docs/CTCAE_v5_Quick_Reference_5x7.pdf (last accessed Mar 12, 2019).

Attribution of each AE will be determined and coded by the Principal Investigator(s), in collaboration with co-investigators as needed. Attribution to study dietary intervention is categorized as follows:

1=Unrelated 2=Unlikely related 3=Possibly related 4=Probably related 5=Definitely related

AE Grade and Attribution	Dose Modification
Occurring at any time on study	
< Grade 2, any attribution	No dose reduction, proceed as planned
≥ Grade 3, unrelated or unlikely related	No dose reduction, proceed as planned
Occurring during Week 1 or 2 of study	
≥ Grade 3, possibly, probably, or definitely related	
Stop the dietary intervention and continue as follows as soon as possible (within one week) after stopping the study food product:
 
➤ Collect the Week 2 stool sample and study questionnaire. (Participant may send the Week 2 stool sample and Questionnaire by mail or deliver in person to the Prevention Center).➤ Collect the end of study fasting blood draw (originally planned for Week 8), at the Prevention Center➤ Omit all remaining activities. Provide EOS Thank You Letter and Gift Card.
Occurring during Week 3 - 8 of study	
≥ Grade 3, possibly, probably, or definitely related	Reduce the dietary intervention to 15g/day for the remainder of the study. Proceed with stool collection, fasting blood draw, and all other data collection as originally planned.
If at any time after dose reducing to 15g/day during Week 3-8 the participant experiences new or continuing ≥ grade 3 AE(s) that are possibly, probably, or definitely related to the study dietary intervention	
Stop the dietary intervention and continue as follows as soon as possible (within one week) after stopping the study food product:
 
➤ Collect the end of study stool sample and study questionnaire (originally planned for Week 8). (Participant may send stool sample and Questionnaire by mail or deliver in person to the Prevention Center).➤ Collect the end of study fasting blood draw (originally planned for Week 8), at the Prevention Center➤ Provide EOS Thank You Letter and Gift Card.

Randomized, Controlled Trial of Resistant Starch in Stage I-III Colorectal Cancer Survivors Pilot Study: The Fiber for Health After Cancer Study

